6.4 Duration of Therapy

In the case of registration scenario #1, patients will continue on CDK4/6 inhibitor and aromatase inhibitor therapy until disease progression*. At that time, patients will be randomized to receive fulvestrant (or exemestane) +/- continuation of CDK4/6 inhibition with ribociclib. In the case of registration scenario #2, patients will be randomized immediately to receive fulvestrant (or exemestane) +/- continuation of CDK4/6 inhibition with ribociclib.

After randomization, in the absence of treatment delays due to adverse event(s), treatment may continue until

one of the following criteria applies:

- Disease progression
- Inter-current illness that prevents further administration of treatment
- Unacceptable adverse event(s)
- Patient decides to withdraw from the study
- General or specific changes in the patient's condition render the patient unacceptable for further treatment in the judgment of the investigator. **OR**
- Pregnancy
- Removal by Sponsor (e.g., unblinding by Sponsor-Investigator).

In the absence of one of the events listed above, there is no pre-defined limit on the number of potential cycles.

* In the case of registration scenario # 1, some patients may discontinue treatment in the pre-randomization phase due to events other than disease progression, including those listed above. (i.e. unacceptable toxicity, patient decides to withdraw from the study, etc.). Those patients will come off study prior to randomization and will not be evaluable for the primary outcome.

6.5 Duration of Follow up

The duration of follow up will vary depending on the registration scenario under which the patient is enrolled as well as the interval between treatment initiation and disease progression. Patients will have an end of treatment visit approximately 4 weeks after removal for any of the specified reasons listed above. Patients will no longer be formally followed after completion of the off-treatment visit, unless adverse event(s) occur that require subsequent follow-up (i.e. unresolved AEs). All adverse events, both serious and non-serious, and deaths that are encountered during the study and within 30 days of the last study intervention should be followed. See Section 8.2.

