Scenario #2: At the time of disease progression while being treated with a CDK4/6 inhibitor (ribociclib **or** palbociclib **or** abemaciclib)+ AI, tamoxifen or fulvestrant

In scenario #1, the study will provide patients with ribociclib + letrozole, but patients will not be randomized until they demonstrate objective evidence of disease progression on treatment. If the patient has previously received letrozole, an alternative AI can be prescribed but will not be provided by the study, i.e. administered as standard of care (ribociclib and letrozole will still be provided by the study). Patients are allowed to have received 4 consecutive weeks of an aromatase inhibitor prior to protocol registration for scenario 1. In scenario #2, patients will be randomized after registration.

At randomization, patients will be assigned to one of the two arms in a 1:1 ratio: 1) Fulvestrant (or exemestane) + ribociclib **or** 2) Fulvestrant (or exemestane) + placebo. Fulvestrant will be given as a 500 mg dose intramuscularly (IM) every 2 weeks for 3 times (loading dose) and then every 4 weeks, as per standard of care. Exemestane will be given as 25 mg orally daily, as per standard of care. The investigational drug ribociclib will be given as 600 mg daily, 3 weeks on/1 week off. Placebo will be administered on the same schedule. For all patients, ribociclib/placebo will be supplied by the study. Fulvestrant or exemestane will be given, as standard of care.

If patient received prior fulvestrant, exemestane must be the hormone therapy backbone in the randomization. If patient received prior exemestane, fulvestrant must be the hormone therapy backbone in the randomization. If neither has been administered, selection of fulvestrant or exemestane in the randomization will be per investigator discretion.

Accrual Target: N= 120 randomized, evaluable patients. Patients will be accrued from 11 academic medical centers in the US, with a goal of completing accrual in two years.

We will ensure that neither registration scenario contains > 60% (N=80) of total study accrual.

Patients will receive treatment on study until disease progression, unacceptable toxicity, or death or withdrawal from study based on patient choice or treating physician's discretion. Every effort will be made to follow patients for primary and secondary outcomes regardless of treatment discontinuation for any reason. Crossover is not built into the study.

Evaluations

Safety Assessment:

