6.2.3. Exemestane

Exemestane is FDA-approved for the treatment of metastatic hormone receptor positive breast cancer. It does not require specific prophylactic or supportive regimens. It can be administered with or without food.

6.2.4 Treatment Duration:

Patients will receive trial treatment until disease progression, unacceptable toxicity, or death or withdrawal from study based on patient choice or treating physician's discretion. Every effort will be made to follow patients for primary and secondary outcomes regardless of treatment discontinuation for any reason. Crossover is not built into the study.

Patients may voluntarily discontinue from the study treatment for any reason at any time. If a patient decides to discontinue from the study treatment, the investigator must make every effort (e.g. telephone, e-mail, letter) to determine the primary reason for this decision and record this information in the patient's chart and on the appropriate CRF pages. They may be considered withdrawn if they state an intention to withdraw, fail to return for visits, or become lost to follow-up for any other reason.

The investigator should discontinue study treatment for a given patient if, on balance, he/she believes that continuation would be detrimental to the patient's well-being. Patients may voluntarily withdraw from the study or be dropped from it at the discretion of the investigator at any time.

Premature patient withdrawal refers to the point/time when the patient exits from the study prior to the planned completion of all study treatment administration and/or assessments; at this time, all study treatment is discontinued and no further assessments are planned, unless the patient will be followed for progression and/or survival.

Patients may be withdrawn from the study treatment if any of the following occur:

- Adverse Event (Documented episode of ventricular tachycardia, or ventricular fibrillation; Complete heart block (Grade III AV block) or Second degree AV block Mobitz type II)
- Lost to follow-up
- Physician decision
- Progressive Disease
- Study terminated

Patients must be withdrawn from the study treatment if any of the following occur:

- Pregnancy
- Death
- Subject/Guardian decision

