6.5.1 Post-treatment Follow-up Assessments (Progression-Free Survival and Overall Survival)

After end of treatment, patients will be followed for Overall Survival. Survivor information may be collected by methods that include, but are not limited to, telephone, e-mail, mail, or retrieved from online or other databases (eg, Social Security indexes). In addition, the start of another anticancer therapy will be recorded. For those patients who discontinue ribociclib for any reason other than radiographic disease progression, CT (with contrast) or MRI scans should be completed to further assess disease progression (per RECIST, Version 1.1), until the subject begins a new anti-cancer treatment or death. Refer to the [Schedule of Events](#) for appropriate assessments during post-treatment follow-up. Patients will no longer be followed for survival after the study is officially closed, which we anticipate will be approximately 2.5 years after the last patient has accrued.

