11.1.4.3 Evaluation of Best Overall Response

The best overall response is the best response recorded from the start of the treatment until disease progression/recurrence (taking as reference for progressive disease the smallest measurements recorded since the treatment started). The patient's best response assignment will depend on the achievement of both measurement and confirmation criteria.

For Patients with Measurable Disease (*i.e.*, Target Disease) +/- Non-Target Disease

Target Lesions	Non-Target Lesions	New Lesions*	Overall Response	Best Overall Response when Confirmation is Required*
CR	CR	No	CR	≥4 wks. Confirmation**
CR	Non-CR/Non-PD	No	PR	≥4 wks. Confirmation**
CR	Not evaluated	No	PR	
PR	Non-CR/Non-PD/not evaluated	No	PR	
SD	Non-CR/Non-PD/not evaluated	No	SD	Documented at least once ≥4 wks. from baseline**
PD	Any	Yes or No	PD	no prior SD, PR or CR
Any	PD***	Yes or No	PD	
Any	Any	Yes	PD	

* See RECIST 1.1 manuscript for further details on what is evidence of a new lesion. ** Only for non-randomized trials with response as primary endpoint. (Not applicable in this trial). *** In exceptional circumstances, unequivocal progression in non-target lesions may be accepted as disease progression.
 
Note: Patients with a global deterioration of health status requiring discontinuation of treatment without objective evidence of disease progression at that time should be reported as “symptomatic deterioration.” Every effort should be made to document the objective progression even after discontinuation of treatment, based on intention to treat analysis.
				

For Patients with Non-Measurable Disease Only (*i.e.*, Non-Target Disease)

Non-Target Lesions	New Lesions	Overall Response
CR	No	CR
Non-CR/non-PD	No	Non-CR/non-PD*
Not all evaluated	No	not evaluated
Unequivocal PD	Yes or No	PD
Any	Yes	PD

* ‘Non-CR/non-PD’ is preferred over ‘stable disease’ for non-target disease. As SD is increasingly used as an endpoint for assessment of efficacy in some trials, to assign this category when no lesions can be measured is not advised.
		

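### Section 6.5 ends formal follow-up at the off-treatment visit, contradicting 6.5.1 and 6.2.4, and neither calendar schedules the post-treatment scans that 6.5.1 requires for PFS

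*Combined protocol and SAP*

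**What the plan says.** Section 6.5 places an end-of-treatment visit about 4 weeks after removal and then states: "Patients will no longer be formally followed after completion of the off-treatment visit". Its only exception is adverse events that need further follow-up.

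Other current text says the opposite:

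- **Section 6.5.1** follows patients for overall survival. It also asks for CT or MRI scans, read by RECIST 1.1, "For those patients who discontinue ribociclib for any reason other than radiographic disease progression". These scans continue "until the subject begins a new anti-cancer treatment or death". Survival follow-up ends at study closure, "which we anticipate will be approximately 2.5 years after the last patient has accrued".
- **Section 6.2.4**, and the Synopsis in the same words: "Every effort will be made to follow patients for primary and secondary outcomes regardless of treatment discontinuation for any reason". Section 6.2.4 also says that no assessments are planned after premature withdrawal "unless the patient will be followed for progression and/or survival".
- **Section 11.1.4.3**, in its note on symptomatic deterioration: "Every effort should be made to document the objective progression even after discontinuation of treatment".

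Section 6.5.1 states no scan interval and sends the reader to the Schedule of Events. In Tables 10.1 and 10.2 scans are tied to every third treatment cycle, and the last scan mark is in the End-of-Treatment column. The only later item is contact every 12 weeks for survival (footnote N of 10.1, footnote L of 10.2).

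**The concern.** The primary endpoint is PFS from randomization to locally assessed progression or death (Sections 1.2.1 and 13.1), analysed by intention to treat. That analysis needs tumour assessments to continue in patients who stop treatment without progression.

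Two sites could each follow the protocol and treat the same patient differently. One, following 6.5 or the calendar, stops imaging a patient who left for toxicity or deterioration. The other, following 6.5.1, continues. Survival contact should still find deaths, but progressions after the End-of-Treatment scan can be missed. If stopping is related to prognosis, or differs by arm, the resulting censoring may be informative.

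Section 13.1 plans an interval-censored analysis and a summary of early discontinuations. These can describe the gap, but they cannot replace scans that were never done.

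**Working it through.** **1. The texts side by side**

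| Place | After a stop without progression |
|---|---|
| 6.5 | Formal follow-up ends, except for adverse events |
| 6.5.1 | Scans until new treatment or death; survival follow-up |
| Synopsis, 6.2.4 | Follow for primary and secondary outcomes |
| 11.1.4.3 | Document objective progression |
| Calendars 10.1, 10.2 | No scan after End of Treatment; survival contact only |

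Section 6.5 is the outlier in wording. The calendars are silent where 6.5.1 relies on them. No order of precedence is stated.

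**2. The plan's own power figure**

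Inputs from Section 13.1: medians 3.8 and 6.5 months, one-sided 2.5%, 80% power, N = 120. Allocation is 1:1.

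- Hazard ratio = 3.8/6.5 = 0.585.
- Events needed (Schoenfeld) = 4(1.960 + 0.842)² / [ln(3.8/6.5)]² = 108.95, so 109.
- Expected events per arm = 60 × {1 − [exp(−λF) − exp(−λ(A+F))] / (λA)}, with λ = ln 2/median. A = 24 months (Synopsis: "with a goal of completing accrual in two years") and F = 30 months (closure in 6.5.1). The two arms together give 119.1.

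Schoenfeld power is 80.0% at 109 events and 83.4% at 119.1, so the stated 80% is reproduced at about 109 events. F = 30 months applies the survival closure to PFS, because no PFS cut-off is stated.

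**3. How many patients are affected**

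The documents give two adverse-event stop rates: 2% (Section 2.3, palbociclib plus fulvestrant) and 6% (Section 8.1, phase I ribociclib monotherapy). Of 120 patients this is 0.02 × 120 = 2.4 to 0.06 × 120 = 7.2.

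**4. Effect on the test**

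Simulation with 100,000 trials per case compared the same trials with and without post-stop scans. Assumptions, none of them in the documents:

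- PFS is exponential, and every PFS event is a progression;
- the stop falls uniformly between 0.5 and 4 months;
- one scan follows 1 month later and then none, with censoring at that scan;
- the hazard after the stop is unchanged (×1) or doubled (×2).

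| Stops, ribociclib/placebo | Hazard after stop | Power, followed | Power, not followed | Change (points) |
|---|---|---|---|---|
| 2%/2% | ×1 | 82.0% | 81.4% | −0.6 |
| 6%/2% | ×1 | 82.0% | 80.6% | −1.4 |
| 6%/2% | ×2 | 78.7% | 80.1% | +1.4 |
| 6%/6% | ×1 | 82.0% | 79.8% | −2.2 |

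Across all cases with F = 30 months, 1.3 to 6.2 progressions are lost. One-sided type I error is 2.4 to 2.7% without the scans and 2.0 to 2.7% with them.

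**5. Cross-check without simulation**

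119.1 − 6.2 = 112.9 events. Schoenfeld power is 81.2% at 112.5 events and 81.8% at 114, against 83.4% at 119.1. That is again a loss of about 2 points.

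**The case against.** The strongest reply is that the documents largely settle the matter themselves. Section 6.5.1 sits directly under 6.5, is headed for PFS and overall survival, and gives the scan duty, modality, criteria and end points. The Synopsis, 6.2.4 and 11.1.4.3 agree with it. The sentence in 6.5 leads into adverse-event follow-up and can be read as ending visits only. The interval is not wholly absent either: the Synopsis, 11.1 and 13.1 all use assessment about every 12 weeks.

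Most of this stands as evidence of intent, and it means that the repair is short. It does not remove the defect. Section 6.5 carves out only adverse events. The 12-week rhythm is written in treatment cycles. A site that follows the cross-reference in 6.5.1 finds no scan to perform.

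It is also fair to say that the rates are imperfect. The 6% comes from monotherapy at 50 to 1200 mg in mixed tumours, and the 6%/6% case applies it to placebo patients too. The simulation does not end scanning at new therapy, as 6.5.1 does, so it overstates what is lost.

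Finally, the remedy comes late. This version is dated February 2024, Scenario 1 is closed, and patients unblinded on treatment at the end of August 2023 no longer follow the calendar (Sections 6.6 and 10.3). That limits its reach, but the exemption in 6.6 covers patients continuing treatment, not those who stopped earlier without progression.

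**Conclusion.** The contradiction is certain and lies in current text. Following 6.5 or the calendars exactly would drop scans that 6.5.1 requires for the primary endpoint. The likely numerical effect is small: about 1 to 6 unseen progressions, a power change of about 2 points or less, and type I error near 2.5%. This rests on the two documented adverse-event stop rates, the assumed stop timing and hazard, and censoring at the last scan; Section 13.1 gives no explicit censoring rule. The direction is unknown, since the table shows both signs. Stops for deterioration have no documented rate and lie outside these figures.

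A reader might infer more, in two ways that the documents do not support:

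- **That the trial runs short of events.** With an assumed 6 months of follow-up after the last patient, 104.1 events are expected against 109. But no such cut-off is stated. Section 13.1 also gives a 3-month effect (3.8 against 6.8 months), which needs 93 events, with 103.3 expected even at 6 months. Section 6.2 plans 66 per arm, or 132, which gives 104.1 × 132/120 = 114.5.
- **That missed progressions replaced by later death dates would seriously damage power or type I error.** This needs a progression-to-death interval that the documents do not give. Subtracting the two medians of the fulvestrant dose trial in Section 2.5 (26.4 − 6.5 = 19.9 months) does not yield a median interval. It also ignores that 6.5.1 ends scanning at new therapy.

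**What to change.** 1. Reword the sentence in Section 6.5 so that it agrees with 6.5.1, 6.2.4 and the Synopsis and does not end progression and survival follow-up.
2. Add to Tables 10.1 and 10.2 the post-treatment tumour assessment that 6.5.1 already requires for patients who stop without progression. Use the protocol's own interval of about 12 weeks and the end points in 6.5.1 (new anti-cancer treatment or death).
3. Correct footnote N of Table 10.1 and footnote L of Table 10.2. They cite Section 6.6 for the 2.5-year closure, which is stated in 6.5.1.

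The cost is text edits plus some scan collection after treatment stops. Because 6.5.1 sets no interval now, a fixed row may mean more scans than some sites perform. The main remaining beneficiaries are patients who stopped without progression and have not started new therapy. The sponsor also gains a clear record of which post-stop scans were required when missing ones are interpreted.

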6.5.1 Post-treatment Follow-up Assessments (Progression-Free Survival and Overall Survival)

After end of treatment, patients will be followed for Overall Survival. Survivor information may be collected by methods that include, but are not limited to, telephone, e-mail, mail, or retrieved from online or other databases (eg, Social Security indexes). In addition, the start of another anticancer therapy will be recorded. For those patients who discontinue ribociclib for any reason other than radiographic disease progression, CT (with contrast) or MRI scans should be completed to further assess disease progression (per RECIST, Version 1.1), until the subject begins a new anti-cancer treatment or death. Refer to the [Schedule of Events](#) for appropriate assessments during post-treatment follow-up. Patients will no longer be followed for survival after the study is officially closed, which we anticipate will be approximately 2.5 years after the last patient has accrued.

6.6 Criteria for Removal

Patients will be removed from study when any of the criteria listed in Section 6.4 applies. The reason for study removal and the date the patient was removed must be documented in source documentation and the Case Report Form. Patients continuing study treatment following unblinding by the Sponsor-Investigator will be treated as per standard of care and therefore will no longer be required to follow the study calendar or complete any of the study assessments that are not part of standard of care. Following unblinding by the Sponsor-Investigator, study teams will no longer be required to enter data into the database aside from SAEs and patient status updates (in the Screening/Enrollment tab in Velos).

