The table below applies to Scenario 2 patients who were Actively receiving treatment when unblinded by the Sponsor-Investigator at the end of August 2023, due to the expiration and discontinuation of the Novartis manufactured placebo for this study. Guidance was provided to all study sites noting that all patients that are Active/On Treatment on scenario 2 will undergo an unblinding process following which patients will continue to receive the assigned treatment: patient who received Ribociclib will continue to do so and patients who received Placebo will continue to receive the endocrine treatment alone, as part of the study. Please note, the study does not allow for crossover between the study groups.

	Patient Visit ¹ (ongoing)
SAE ²	X
Disease Progression ³	X
Patient Status on Study ⁴	X

1. Visit frequency should be determined as per standard of care.
2. All SAEs experienced by patients receiving study treatment should be reported as per section 8.2.7 and entered in the Velos database.
3. Disease Progression should be documented in the patient statuses in velos, as reason for removal from study treatment, if applicable.
4. Any update to the patients' stua y status should be entered in Velos.

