13.6 Unblinding Procedures

The Investigator, the study site personnel, and the subject will remain blinded to each subject's treatment with Ribociclib/Placebo throughout the course of the study.

Access to blinded subject treatment information during the study will be made available to the investigator/limited site personnel, only if identification of the study drug is required for a medical emergency. Medical emergency includes a situation in which the knowledge of the specific blinded treatment will affect the immediate management of the subject/subject's conditions, or when knowledge of previous treatments is required for enrollment in another trial, or as part of managing a serious adverse event.

Investigators should note that emergency unblinding is reserved only for emergency situations where lack of knowledge about the actual study drug treatment interferes with appropriate emergency management. **The occurrence of an SAE or progressive disease should not routinely precipitate the immediate unblinding of the label.**

In the event of a Suspected Unexpected Serious Adverse Reaction (SUSAR) (see Section 8.2.8) related to the blinded treatment, the subject's treatment code will usually be

broken before reporting to health authorities and central ethics committees in an unblinded fashion. In compliance with 21 CFR 312 on the collection and verification of presentation of AE/reaction reports arising from clinical trials on medicinal products for human use, investigators and persons responsible for the ongoing conduct of the study will not usually receive unblinded copies of SUSAR reports, unless unblinded information is judged necessary for safety reasons.

At the end of August 2023, the Placebo drug manufactured and provided by Novartis, expired and an unblinding of the Scenario 2 patients who were on treatment at the time was required. Guidance was provided to all study sites noting that all patients that are Active/On Treatment on scenario 2 will undergo an unblinding process following which patients will continue to receive the assigned treatment: patient who received Ribociclib will continue to do so and patients who received Placebo will continue to receive the endocrine treatment alone, as part of the study. Please note, the study does not allow for crossover between the study groups.

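### After the August 2023 unblinding, sites need not enter the scan dates and RECIST basis behind PFS, Section 13.1 plans nothing for open-label progression calls, and the sections conflict on study status

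*Combined protocol and SAP*

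**What the plan says.** The primary endpoint is PFS from randomization, with objective progression judged locally (1.2.1). Section 13.1 calls the trial double-blinded, sets imaging about every 12 weeks under RECIST 1.1, and analyses PFS by intention to treat with a log-rank test. Section 10.2 adds RECIST restaging signed by the investigator after each scan.

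Sections 10.3 and 13.6 report the unblinding of all Scenario 2 patients on treatment at the end of August 2023. For them:

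- Section 6.6: they "will no longer be required to follow the study calendar or complete any of the study assessments that are not part of standard of care", and "study teams will no longer be required to enter data into the database aside from SAEs and patient status updates".
- Section 10.3, Table 3: "Visit frequency should be determined as per standard of care". Progression stays on the list of items, but as a status: "Disease Progression should be documented in the patient statuses in velos, as reason for removal from study treatment".

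On study status, 6.6 opens with "Patients will be removed from study when any of the criteria listed in Section 6.4 applies", and the 6.4 list includes "Removal by Sponsor (e.g., unblinding by Sponsor-Investigator". Section 13.6 says instead that "patients who received Placebo will continue to receive the endocrine treatment alone, as part of the study", and that ribociclib patients stay on ribociclib. Section 6.2.4 promises: "Every effort will be made to follow patients for primary and secondary outcomes regardless of treatment discontinuation for any reason".

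**The concern.** A locally assessed PFS endpoint draws its credibility from blinded assessors, a fixed scan schedule and recorded RECIST assessments. For these patients the first has ended and the other two are no longer required by the protocol. The statistical section was not adapted: it never mentions the unblinding, gives no PFS data cut-off, and does not distinguish progressions called blind from those called open-label.

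Two things are at stake. One is whether the primary result can be shown to be robust to open-label calls. The other is whether sites keep following these patients for PFS at all, since one reading of 6.4 and 6.6 takes them off study.

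**Working it through.** **The design figure.** Inputs from 13.1: medians 3.8 and 6.5 months, one-sided alpha 2.5%, power 80%, N=120. HR = 3.8/6.5 = 0.585. Schoenfeld events = 4(1.960+0.842)²/(ln 0.585)² = 4×7.85/0.288 = 109. With uniform accrual over a months and follow-up f, the event fraction is 1 − [e^(−λf) − e^(−λ(a+f))]/(λa), with λ = ln 2/median. At a=24 (the Synopsis goal) and f=9 (an assumption; no PFS follow-up is given) it is 0.956 and 0.862, mean 0.909, and 109/0.909 = 120. The plan's N is reproduced. Since 109/120 = 91%, nearly every PFS event is needed, late ones included.

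**What 6.6 and 10.3 leave.**

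- Kept: standard-of-care visits and any scans that belong to them, a progression status, and the date of and reason for removal.
- No longer required to be entered: scan dates, lesion measurements or RECIST basis, and the last progression-free assessment.

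**What that could do to the test.** The documents do not give the number unblinded, the end of accrual or the PFS cut-off, so this is an illustration. Simulation, 8,000 runs per cell (Monte Carlo SE 0.2–0.3 points for error, 0.4–0.5 for power): 60 per arm, uniform 24-month accrual, exponential PFS rounded up to 12-week scans, everyone followed to progression, rejection at z < −1.96. Eligible for unblinding: 93 random patients, that is 120 minus the 27 Scenario 1 patients in 6.2, assuming that all 27 are among the 120. Exposed means eligible with progression recorded after the unblinding. Late means recorded one scan late. The interval-censored test uses the pooled nonparametric maximum likelihood estimate with log-rank-type scores.

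| Months from last randomization to unblinding | 0 | 2 | 5 | 8 | 12 |
|---|---|---|---|---|---|
| Exposed, no true effect (mean of 120) | 26.8 | 19.1 | 11.0 | 6.3 | 3.1 |
| Log-rank error %, all exposed ribociclib progressions late | 8.5 | 6.5 | 4.2 | 3.5 | 2.5 |
| Same, half of them late | 4.9 | 4.4 | 3.2 | 2.9 | 2.3 |
| Interval-censored error %, all late, interval from last pre-unblinding scan to status date | 4.0 | 3.4 | 2.7 | 2.6 | 2.4 |
| Interval-censored error %, scan dates known, every ribociclib call one scan late | 8.0 | 6.1 | 3.8 | 3.1 | 2.4 |
| Interval-censored power %, 3.8 vs 6.5 months, status-date intervals | 69.5 | 73.9 | 75.9 | 78.3 | 79.6 |

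The remaining cases:

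- Equal delay in both arms: log-rank error 2.2–2.6%, no inflation. This is the only change that the documents describe.
- Placebo arm alone late: 0.7–2.1%, conservative.
- Interval-censored power with scan dates entered: 80.0–81.2%.
- With 80 eligible (the scenario cap printed in the Synopsis), the first log-rank row becomes 7.5, 5.4, 4.1, 3.1, 2.9%.
- Repeat simulations of the 8.5% cell ranged from 7.5% to 9.0%.

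**Study status.** Read literally, 6.4 with the first sentence of 6.6 removes a patient unblinded by the sponsor-investigator. The third sentence of 6.6, Table 3 and 13.6 all assume that the same patient continues. No passage censors PFS at the unblinding.

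**The case against.** The strongest reply is that little is lost and much is already covered.

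- **Scans may continue.** Section 6.6 waives only what lies outside standard of care and still asks for the removal date. Section 6.5.1 asks for scans when ribociclib stops without radiographic progression, and 11.1.4.3 asks for efforts to document objective progression after discontinuation. This stands: the endpoint's definition has not been relaxed, only its schedule and data entry.
- **The interval-censored log-rank in 13.1 is already promised**, especially for differing schedules and considerable missing data. This largely stands. It holds the worst delay case to 4.0%. But it works best with dates that 6.6 no longer requires, and even with those dates it does not correct a shifted progression call (8.0% in the extreme case).
- **Independent review (11.1.7) may include progressive disease**, since the response tables list it as an overall response. That reading is possible. The primary endpoint nevertheless remains local assessment.
- **Other sensitivity analyses are allowed by 13.1.** They are permitted, but none is specified for the unblinding.
- **The status conflict is a drafting slip.** Probably so, and wording alone resolves it.

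A reader might infer that primary PFS is biased in favour of ribociclib, or that PFS data after August 2023 are lost. The documents support neither. Inflation needs an assumed lateness in one arm only. Whether any post-unblinding event enters the primary test depends on an unstated cut-off; if that fell before the unblinding, none does.

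**Conclusion.** The gap in the text is certain; its effect on the result is not known. Three things hold on the wording alone: 6.6 drops required entry of the dates and RECIST basis behind later PFS events; 13.1 has no analysis that separates blinded from open-label calls; and 6.4/6.6 contradict 10.3/13.6 on whether these patients remain on study.

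The error figures of about 8–9% are an upper illustration. They need unblinding on the day of the last randomization and every exposed ribociclib-arm progression recorded late, with none late on placebo. By 12 months after the last randomization the effect is close to nil. What needs no arm-specific assumption is the power loss of the interval-censored analysis without scan dates, about 11 points falling to 1. That concerns a supporting analysis, not the primary test. The point should be fixed, but it does not invalidate the primary analysis.

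**What to change.** 1. Amend 6.6 so that sites enter, from existing records, the date and RECIST basis of each post-unblinding progression and the dates of intervening scans.
2. State in 13.1 that intention-to-treat PFS with all follow-up remains primary. Report by arm the number of patients unblinded on treatment and the number of PFS events after unblinding.
3. If between-arm PFS has not yet been analysed, pre-specify one supportive estimate that censors PFS at the last RECIST assessment on or before the unblinding, with the same calendar cut in both arms. Give it as a hazard ratio with confidence interval, not as a second test.
4. Reconcile 6.4/6.6 with 10.3/13.6 on whether these patients remain on study for PFS.

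The cost is wording, a little retrospective data entry, one analysis and two counts per arm. The primary analysis loses no power. The supportive estimate is blunt: applied to everyone, it also cuts Scenario 1 follow-up, which this unblinding did not touch. At 3.8 versus 6.5 months it censors about 35, 27, 18, 12 or 7.5% of patients for unblinding 0, 2, 5, 8 or 12 months after the last randomization. Its power is about 64–65, 70, 74–76, 77–78 or 79–80%, against 81–83% with full follow-up. That is why it should be read as an estimate. It is still needed, because entered scan dates alone do not guard against shifted calls; in the simulated shifted-call case the cut kept error at 2.3–2.7%.
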